9.1. Hypotheses and Acceptance Criteria

Vaccine efficacy (VE) is defined as $VE = 1 - RR$, where RR is the relative risk in SA4Ag compared to placebo, ie, the proportion of SA4Ag recipients meeting the primary endpoint relative to the proportion of placebo recipients meeting the primary endpoint. SA4Ag will be compared to placebo testing the hypotheses $H_0: VE \leq 20\%$ vs $H_a: VE > 20\%$.

A conditional power-based⁵⁹ futility procedure will be implemented during case accrual. Periodically the current estimate of VE will be assessed, and there will be a calculation of the power of the study at its planned completion at 48 cases conditional upon that value. The DMC will review the calculation and if the conditional power of the study is low, corresponding to the critical case splits shown in Table 15, futility may be declared and the study may cease enrollment. It is anticipated that this procedure will be implemented after approximately 10 and 15 cases have been accrued, and also at the time of the interim analysis at 24 cases. The assessments after 10 and 15 cases can only result in a possible declaration of futility, not efficacy; as such, there is no impact on the overall alpha level of the study. Full details of the conditional power-based futility procedure will be provided in the SAP.

An interim analysis will be performed after accumulating 24 per-protocol cases for review by the DMC. Only the primary endpoint, defined in [Section 9.3.2](#), will be examined. The probability of the number of vaccine cases will be calculated using the binomial distribution with 24 trials and $p = 0.444$ because, under the null hypothesis and 1:1 randomization, the probability that a selected case is from SA4Ag is 0.444. If the number of vaccine cases is 3 or fewer, then the null hypothesis will be rejected in favor of the vaccine. If significant efficacy is observed at the interim analysis, the study may continue to enroll subjects to ensure that the study will provide sufficient safety data for vaccine licensure.

A 99.7% confidence interval (CI) will be obtained for VE. The confidence level is obtained from the O'Brien-Fleming⁶⁰ alpha levels, explained below. If the study does end for efficacy at interim analysis, events collected subsequent to the interim analysis will be reported in a supplement in a similar manner to that described in Whitehead⁶¹ for overrunning data, described below. Otherwise, the study will continue to the accumulation of 48 cases.

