Once 48 per-protocol cases have accumulated SA4Ag will be compared to placebo for the primary endpoint, testing the hypotheses $H_0: VE \leq 20\%$ vs $H_a: VE > 20\%$. SA4Ag will be deemed efficacious if it has 14 cases or fewer out of a total of 48 cases (point estimate of $VE = 58.8\%$ and 2-sided lower 95.1% confidence limit $> 20\%$).

Although the final analysis is expected to have 48 cases, it is possible that additional potential cases will be present in the adjudication system (entered into the adjudication electronic case report form [eCRF]) on the same day that the 48th per-protocol case is reported to the EAC. These additional cases will be included in the final analysis, if confirmed as cases by the EAC. Therefore, the time order of case entry into the adjudication system will determine which cases will be included in the analysis. O'Brien-Fleming boundaries will be maintained for decisions regarding VE. In other words, in the event that more than 48 cases are available for the final analysis, the null hypothesis will be rejected if the lower bound of the 95.1% confidence interval is greater than 20%.

Similarly, although the interim analysis is expected to have 24 cases, it is possible that additional potential cases will be present in the adjudication system (entered into the adjudication eCRF) on the same day that the 24th per-protocol case is reported to the EAC. These additional cases will be included in the interim analysis, if confirmed as cases by the EAC. The time order of case entry into the adjudication system will determine which cases will be included in the interim analysis. O'Brien-Fleming boundaries will be maintained for decisions regarding VE. In other words, in the event that more than 24 cases are available for the interim analysis, the null hypothesis will be rejected if the lower bound of the 99.7% confidence interval is greater than 20%. Even if more than 24 cases are included in the interim analysis, the final analysis will be performed on 48 cases, unless additional cases are available as described in this section. Similar rules for case inclusion will apply to the futility analyses planned at 10 and 15 per-protocol cases.

No multiplicity adjustments will be applied to the secondary endpoints. All other secondary endpoints will be evaluated at a 2-sided alpha level of 0.05.

[figure not shown]

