9.3.2. Analysis of the Primary Endpoint

For the primary objective, the efficacy of SA4Ag will be based on the number of per-protocol subjects in each vaccine group with postoperative *S aureus* BSI and/or deep incisional or organ/space SSI occurring within 90 days of elective open posterior spinal fusion procedures with multilevel instrumentation, as confirmed by the EAC. In case of multiple occurrences meeting the primary endpoint from the same subject, only the first episode will be used to calculate the VE.

Examples of the estimated efficacy and associated CIs for a selected number of SA4Ag cases are presented in Table 15.

Table 15. Estimated Efficacy and Associated Confidence Intervals for a Select Number of SA4Ag Cases

Analysis Stage	Total Cases	SA4Ag Cases	Estimated Efficacy and Confidence Interval ^a	Comments
Futility	10	7	-133% (-1298%, 46.7%)	Conditional power <20%; possible futility declaration
	15	9	-50% (-412%, 52.3%)	Conditional power <20%; possible futility declaration
	24	11	15.4% (-105%, 66%)	Conditional power <20%; possible futility declaration
Interim	24	3	85.7% (24.9%, 99.0%)	Max number of SA4Ag cases that permits inference that true VE is >20%

Table 15. Estimated Efficacy and Associated Confidence Intervals for a Select Number of SA4Ag Cases

Analysis Stage	Total Cases	SA4Ag Cases	Estimated Efficacy and Confidence Interval ^a	Comments
Final	48	8	80.0% (56.5%, 91.9%)	Estimated efficacy = 80%
	48	11	70.3% (40.3%, 86.4%)	Estimated efficacy =70%
	48	14	58.8% (21.0%, 79.6%)	Max number of SA4Ag cases that permits inference that true VE is >20%

Abbreviations: N/A = not applicable; VE = vaccine efficacy.

- a. 99.7% confidence level for interim analysis; 95.1% confidence level for final analysis; 95% confidence level for futility.

The findings at the time of the final analysis will serve as the primary basis for efficacy conclusions.

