**Table 1. Conditional Power at Planned Futility Analyses**

Total Cases	Minimum SA4Ag Cases for futility	Estimated VE (%)	Conditional Power a
10 b	7	-133% (-1298%, 46.7%)	6.9%
15	9	-50% (-412%, 52.3%)	19.4%
24	11	15.4% (-105%, 66%)	16.1%

VE = vaccine efficacy.

- Power of the study to detect  $VE > 20\%$  at the final analysis at 48 cases, conditional upon the cases observed so far, and assuming  $VE = 70\%$  following the futility check.
- For 10 total cases, the SA4Ag case criterion and conditional power were calculated before protocol amendment 4 based on the previous study hypothesis.

Conditional power will be evaluated under the assumption that after the futility check, vaccine efficacy is 70%, as in the main study design assumptions. For operational reasons, the futility checks may occur at slightly different case totals from those planned; in that case, the futility rule of less than 20% conditional power will apply.

The interim efficacy analysis will be performed after accumulating 24 PP cases. Only the primary endpoint, defined in [Section 6.1.1](#), will be examined. The probability of the number of vaccine cases will be calculated using the binomial distribution with 24 trials and  $\pi = 0.444$  because, under the null hypothesis and 1:1 randomization, the probability that a selected case is from the SA4Ag cohort is 0.444. If the number of vaccine cases is 3 or fewer, then the null hypothesis will be rejected in favor of the vaccine. A 99.7% confidence interval (CI) will be obtained for VE.

Once 48 PP cases have accumulated, SA4Ag will be compared to placebo in the primary endpoint. SA4Ag will initially be compared to placebo, testing the hypothesis  $H_0: VE \leq 20\%$  vs  $H_a: VE > 20\%$ . SA4Ag will be deemed efficacious if it has 14 cases or fewer out of a total of 48 cases (point estimate of  $VE \geq 58.8\%$  and 2-sided lower 95.1% confidence limit  $> 20\%$ ).

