The interim analysis will be performed on the first 24 PP cases and the final analysis will be performed on the first 48 PP cases. Although the final analysis is expected to have 48 cases, it is possible that additional potential cases will be present in the adjudication system (entered into the adjudication electronic case report form [eCRF]) on the same day that the 48th per-protocol case is reported to the EAC. These additional cases will be included in the final analysis, if confirmed as cases by the EAC. Therefore, the time order of case notification from the EAC to the sponsor will determine which cases will be included in the analysis. O'Brien-Fleming boundaries will be maintained for decisions regarding VE.

O'Brien-Fleming boundaries will also be maintained if the EAC informs the sponsor of the 25th case (or any further cases) on the same day. It is possible that additional potential cases will be present in the adjudication system. The time order of case notification from the EAC to the sponsor will determine which cases will be included in the interim analysis. Even if more than 24 cases are included in the interim analysis, the final analysis will be performed on 48 cases, unless additional cases are available as described in this section.

The interim analysis will not be revised even if the interim and final case counts do not meet planned values; eg, if the interim analysis is performed with 24 cases, but the final PP analysis has 49 or more cases, the interim analysis will not be revised.

Only the primary endpoint in the PP efficacy population will be subjected to an interim analysis.

The futility analysis will be applied to the primary endpoint only, in the PP efficacy population. After accumulating approximately 10, 15, and 24 primary endpoint cases, the power of the study to reject the original null hypothesis, conditional upon the results accumulated so far, will be calculated. Futility may be declared and the study may cease enrollment, if the conditional power falls below 20%. This will occur if 7 or more vaccine cases are observed out of 10 total cases at the first futility check, or if 9 or more vaccine cases are observed out of 15 total cases at the second futility check, or if 11 or more vaccine cases are observed out of 24 total cases at the third futility check.

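### SAP 8.1.1 says 7 SA4Ag cases out of 10 puts conditional power below 20%; under the SAP's current definition it is 32.3%, and the legacy caveat in Table 1 is not repeated there

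*SAP*

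**What the plan says.** SAP 8.1.1 sets the futility trigger at conditional power below 20%, then gives the splits that meet it. For the first check it says: "This will occur if 7 or more vaccine cases are observed out of 10 total cases at the first futility check". The other splits are 9 of 15 and 11 of 24.

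Protocol 9.1 describes low conditional power as "corresponding to the critical case splits shown in Table 15". The 7/10 row of that table carries the comment "Conditional power <20%; possible futility declaration", as do the 15- and 24-case rows. Protocol 9.1 leaves the method to the SAP: "Full details of the conditional power-based futility procedure will be provided in the SAP".

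SAP 4.2 defines the quantity. It is the power to show VE above 20% at 48 cases, given the cases so far. "Conditional power will be evaluated under the assumption that after the futility check, vaccine efficacy is 70" (per cent). Table 1 there gives 6.9% at 7/10, 19.4% at 9/15 and 16.1% at 11/24. Footnote b qualifies the first row only: "For 10 total cases, the SA4Ag case criterion and conditional power were calculated before protocol amendment 4 based on the previous study hypothesis".

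For a check at any other case total, SAP 4.2 says "in that case, the futility rule of less than 20% conditional power will apply". Protocol 9.1 foresees such totals, because cases entered on the same day may be added: "Similar rules for case inclusion will apply to the futility analyses planned at 10 and 15 per-protocol cases".

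**The concern.** The first-check threshold is presented as the result of applying the 20% rule. Footnote b shows that it was carried over from a superseded design, so it need not satisfy the rule under the present one. The footnote does not say whether it does, and neither document gives a current-design value for 7/10. Someone working from SAP 8.1.1 or protocol Table 15 would report 7/10 as an instance of the 20% rule.

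If it is not one, a prespecified stopping threshold is misdescribed. The first check would also be out of line with the rule that applies when the count is 9 or 11 instead of 10.

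**Working it through.** **Inputs**
- Final success: 14 or fewer SA4Ag cases of 48 (SAP 4.2).
- VE after the check: 70% (SAP 4.2). With 1:1 allocation, the probability that a future case is SA4Ag is p = (1 − VE)/(2 − VE) = 0.3/1.3 = 0.2308. Protocol 9.2 rounds this to 0.230.
- Efficacy at the 24-case interim needs 3 or fewer SA4Ag cases, so it is out of reach once 7 have occurred.

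**Formula.** With x SA4Ag cases out of n, conditional power = P(Bin(48 − n, p) ≤ 14 − x).

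**The plan's own rows, then the neighbouring split**

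| Split | Expression | Result | SAP Table 1 |
|---|---|---|---|
| 9/15 | P(Bin(33, p) ≤ 5) | 19.35% | 19.4% |
| 11/24 | P(Bin(24, p) ≤ 3) | 16.15% | 16.1% |
| 7/10 | P(Bin(38, p) ≤ 7) | 32.3% | 6.9% (legacy) |
| 8/10 | P(Bin(38, p) ≤ 6) | 19.3% | not given |

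The 15- and 24-case rows reproduce, so the method is the SAP's. With p = 0.230 the 10-case values are 32.7% and 19.6%, and the conclusion is the same. The 6.9% cannot be checked, because the documents do not give the full inputs of the earlier design.

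**Could 7 SA4Ag cases meet the rule another way?**
- At a smaller total: the lowest possible value is at 7/7, P(Bin(41, p) ≤ 7) = 23.9%.
- Treating the later futility stops (9/15 and 11/24) as taken: 7/10 gives 24.7%.

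Neither is below 20%.

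**Neighbouring totals.** 8/9 gives 17.2%, 8/11 gives 21.7% and 9/11 gives 11.4%. The first split below 20% is 8 at 8–10 cases, 9 at 11–15, 10 at 16–20 and 11 at 21–25. With the carried-over value, the thresholds at 9, 10 and 11 cases run 8, 7, 9.

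**Consequence for the design.** Exact recursion over 10, 15, 24 and 48 cases, with all stops taken, comparing a first threshold of 7 with 8:

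| Quantity | Threshold 7 | Threshold 8 |
|---|---|---|
| Futility at 10 cases, VE 0% | 17.2% | 5.5% |
| Futility at 10 cases, VE 20% | 9.6% | 2.5% |
| Futility at 10 cases, VE 70% | 0.2% | 0.02% |
| Futility at any check, VE 0% | 73.5% | 73.3% |
| Rejection at VE 20% | 2.22% | 2.22% |
| Power at VE 70% | 87.60% | 87.65% |
| Mean cases, VE 0% | 26.5 | 27.4 |

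The threshold-7 percentages agree with SAP Table 11 within 0.3 percentage points, so Table 11 was run with 7/10. The only 10-case result classified differently is exactly 7/10. Its probability is 11.7%, 7.1%, 0.7% and 0.2% at VE 0%, 20%, 60% and 70%.

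**The case against.** The strongest reply is that SAP 4.2, where the rule is defined, already discloses the legacy origin, and that the action threshold of 7/10 is the same everywhere. On this view only a cross-reference is missing. The disclosure is real, and the 6.9% is a declared carry-over, not a miscalculation. But footnote b does not say that 7/10 fails the 20% rule under the current design, and SAP 8.1.1 states flatly that it meets it.

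A second reply is that protocol 9.1 words conditional power as based on the current VE estimate. Read that way, conditional power at 7/10 is about 7 × 10⁻¹¹, and the Table 15 label is literally true. However, that reading would put the first splits below 20% at 4/10, 6/15 and 9/24 (5.7%, 4.4% and 6.6%), not at 7, 9 and 11. The 15- and 24-case splits fit only the VE 70% definition, and the protocol defers to the SAP for details. What stands is that the protocol wording and the SAP definition differ and should be aligned.

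Third, little depends on it now. Futility is permissive, the operating characteristics hardly move, and SAP 8.1.3.5 records that enrollment ceased when the futility criteria were met at the interim analysis in December 2018. All of this stands. The 24-case row is correct, so nothing here questions that stop.

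**Conclusion.** The concern holds. SAP 8.1.1 and protocol Table 15 describe 7/10 as meeting a 20% rule that it does not meet under the current design: conditional power is 32.3%, and the first qualifying 10-case split is 8/10 at 19.3%. This rests on the SAP's definition (14 or fewer of 48, VE 70% after the check), which reproduces the other two rows.

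The consequence is limited to the accuracy of the record. Type I error and power are essentially unchanged and Table 11 remains valid. Because the study ceased enrollment on prespecified futility criteria, the report should describe those criteria correctly.

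**What to change.** **Preferred.** In SAP 8.1.1 and protocol Table 15, say that 7/10 is a threshold kept from before protocol amendment 4, as footnote b of SAP Table 1 already does. Give its current-design conditional power (32.3%) beside the legacy 6.9%, and remove the below-20% claim for that row only. Align the protocol 9.1 wording on the current VE estimate with the SAP definition of VE 70% after the check. The cost is one sentence in SAP 8.1.1, one note to protocol Table 15 and one clause in protocol 9.1, with no new simulation. If the documents will not be amended again, the same statement can go in the study report.

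**Alternative, only if the rule is to apply prospectively.** Use 8/10 (19.3%) and rerun Table 11. On average this costs about 0.8 more cases if VE is 0% (26.5 to 27.4 as rounded).

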**Table 11. Operating Characteristics of Study Design**

Study Outcome	Assumed Vaccine Efficacy (%)			
	0%	20%	60%	70%
Futility				
at 10 cases	17.0%	9.6%	0.7%	0.2%
at 15 cases	15.7%	9.5%	0.7%	0.2%
at 24 cases	40.9%	34.3%	4.4%	1.0%
at any time	73.6%	53.3%	5.9%	1.4%
Positive Interim Analysis	0.0%	0.1%	5.8%	16.3%
Positive Final Analysis	0.3%	2.2%	54.7%	71.2%
Negative Final Analysis	26.1%	44.4%	33.6%	11.1%
Total Positive Outcomes	0.3%	2.3%	60.5%	87.5%
Total Negative Outcomes	99.7%	97.7%	39.5%	12.5%
Mean no. cases required	26.5	33.0	45.0	43.7

Percentages of study outcomes in 100,000 simulations of the trial under each assumed vaccine efficacy. ‘Positive’ outcomes are where the null hypothesis that VE ≤20% is rejected at either the interim or final analysis. ‘Negative’ outcomes are a declaration of futility or failing to reject the null hypothesis at the final analysis. All percentages rounded to 0.1%.

The analyses of the secondary endpoints, the exploratory efficacy endpoints, and the primary endpoint in the mITT efficacy population will be evaluated at a 2-sided alpha level of 0.05. The proportion of SA4Ag cases divided by total cases will be translated into VE for each endpoint. The upper and lower limits of the associated 95% CI on the proportion will be translated to upper and lower 95% confidence limits on VE.

Subgroup analyses will use the same methodology as described above, but will be performed separately at each level of the subgroup. Some levels of subgroups may be combined before analysis. Subgroups without cases in either vaccine group will not be analyzed.

The subgroup analyses on the primary endpoint from the PP efficacy population will be performed on the 24 cases (if the study ends on interim analysis) or 48 cases (if the study ends as planned). More PP cases may accumulate after the 24 or 48 cases as remaining subjects complete enrollment, so the subgroup analyses will also be repeated with the additional cases.

Endpoint definitions include specified microbiological confirmations. Absence of microbiological confirmation excludes the suspected infection from the endpoint analysis. But if the microbiological tests are not performed (because of lack of sample, lost sample, invalid assay, etc), then the PDI will be considered a missing value for endpoint analyses. PDIs adjudicated as noncases in the presence of sufficient and valid microbiological testing will not be considered missing values. Missing-data sensitivity analyses will be performed for the BSI, SSI, and ISA disease endpoints. The methods for missing-data sensitivity analyses are described in [Handling of Missing Values](#).

Another set of sensitivity analyses will incorporate follow-up time in the efficacy calculation. The variable P will be the proportion of SA4Ag cases divided by the number of all cases. The variable h will be ratio of total follow-up time in the placebo group to the total follow-up time in the SA4Ag group. Follow-up time for any subject is the date of study completion (or dropout or case onset, whichever comes first) minus the date of index surgery, plus 1. Then estimated efficacy will be  $1-hP/(1-P)$ . The efficacy's CI will be obtained by calculating the CI for P, then substituting in the expression. The CI for P will be obtained using the Clopper-Pearson method. The confidence level will be the same as for the indicated endpoint. The method is described in Blackwelder, substituting follow-up time for number of subjects. Follow-up time sensitivity analyses will be performed for the primary and secondary endpoints in both the mITT and PP efficacy populations.

Number needed to treat (NNT) will be calculated as the reciprocal of the proportion of SA4Ag cases minus the proportion of placebo cases. NNT will be calculated for each endpoint. A 95% CI will be obtained for each NNT by obtaining a 2-sided 95% CI on the difference in proportions using the method of Chan and Zhang, then reciprocating the upper and lower limits.

1. If the difference in proportions and both confidence limits are less than zero, then the results will be presented as  $NNT = xx.x (xx.x, xx.x)$ , with the negative signs omitted.

2. If the difference in proportions and both confidence limits are greater than zero, then the results will be presented as number needed to harm (NNH) = xx.x (xx.x, xx.x).
3. If the CI brackets zero, then the results will be presented as NNT (if negative) or NNH (if positive) = xx.x (NNT = xx.x, NNH = xx.x), with any negative signs omitted.
4. If the difference in proportions is exactly zero, then the estimated NNT will be presented as  $NNT = \infty$ .

Statistical analyses for efficacy are summarized in [Section 8.2.1](#).

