6.3. Stage 2: Surgery Stage

The surgery stage of the study covers the period from Visit 2 (index hospital admission) to Visit 6 (Day 180 postoperative evaluation).

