7.1. Efficacy Assessments

7.1.1. PDI Events

All subjects who undergo the index surgical procedure will be monitored for PDIs after surgery until the Day 180 postoperative evaluation.

[figure not shown]
The investigator will review all suspected PDIs against the clinical criteria provided in Appendix 1. Where the clinical criteria are met, the following procedures will be conducted:

- Notify the sponsor that a PDI event has occurred.
- Complete the requirements for a BSI/SSI event ([Section 6.4.2](#)) or an ISA event ([Section 7.1.1.2](#)).
- Report the PDI event in the CRF.

If an infection occurs after discharge from the index hospital, and the infection is managed or treated by a noninvestigator physician or at a nonstudy hospital, the study investigator will contact the treating noninvestigator physician/hospital to obtain the information required (eg, medical or hospital records, clinical, diagnostic, and microbiological data) to determine whether the infection meets PDI clinical criteria. If the clinical criteria are met, the investigator will complete the PDI event report noted above and notify the sponsor.

For the purposes of this study, PDIs will include all the infections listed in Table 6 and Table 7. As shown in Figure 1, the relationships between ISA, BSI, and SSI overlap, insofar as all BSI and SSI, with the exception of superficial SSI, are considered to be ISA disease.

Figure 1. Protocol-Defined Infections (Venn Diagram)

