## 6. ENDPOINTS AND COVARIATES

### 6.1. Efficacy Endpoint(s)

All efficacy endpoint events will be evaluated by the EAC. The EAC will determine whether or not the event meets the case definition criteria, including diagnosis and onset date relative to surgery. Confirmed cases will contribute to the efficacy analyses.

Windows described as “within 90 days” (or “within 180 days”) mean that infections with onset occurring on Days 1-90 (or Days 1-180), inclusive, will be included. Day 1 is the day of the index surgery.

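### The follow-up-time sensitivity analysis counts person-time to Day 180 for the two 90-day endpoints, so unequal dropout after Day 90 moves a 90-day VE

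*SAP*

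**What the plan says.** SAP Section 8.1.1 plans a sensitivity analysis in which VE is 1 - hP/(1 - P), where P is the share of cases that fall in the SA4Ag arm. "The variable h will be ratio of total follow-up time in the placebo group to the total follow-up time in the SA4Ag group". Person-time has a single definition: "Follow-up time for any subject is the date of study completion (or dropout or case onset, whichever comes first", less the date of index surgery, plus 1. For the interval, "The CI for P will be obtained using the Clopper-Pearson method" and is then put through the same expression.

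The scope is stated too: "Follow-up time sensitivity analyses will be performed for the primary and secondary endpoints in both the mITT and PP efficacy populations". SAP Table 17 lists follow-up time as a method for all four of these endpoints, two with a 90-day window and two with a 180-day window.

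The window itself is in SAP Section 6.1, where the 90-day and 180-day labels "mean that infections with onset occurring on Days 1-90 (or Days 1-180), inclusive, will be included". That sentence selects cases and says nothing about person-time. Study completion is the Day 180 visit: in Protocol Section 7.1.1, "All subjects who undergo the index surgical procedure will be monitored for PDIs after surgery until the Day 180 postoperative evaluation", and Protocol Section 6.3 has the surgery stage end at Visit 6. I found no text that truncates follow-up at Day 90.

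**The concern.** Replacing subject numbers by person-time in 1 - hP/(1 - P) makes sense only if the person-time is time at risk of the event being counted. For the 90-day endpoints, roughly half of the planned follow-up (Days 91-180) is time in which no event can count. Two things follow. A subject who leaves after Day 90 has been fully observed for the endpoint, yet still lowers that arm's person-time. A subject who leaves before Day 90 is charged for the lost days up to Day 180, not only for those up to Day 90.

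The main VE formula, 1 - p/(1 - p), uses case counts alone, and I find no other planned efficacy analysis that adjusts for unequal follow-up. If this analysis is to show whether differential dropout matters, it should respond only to dropout that bears on the endpoint.

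**Working it through.** **Inputs.** Final success boundary of 14 SA4Ag cases in 48, 95.1% two-sided interval, null VE of 20% (Protocol Section 9.1; SAP Sections 4.2 and 8.1.1). Allocation 1:1. The only dropout figure in the documents is 10% overall (Protocol Section 9.2), with no split by arm or time, so every split below is an assumption. Person-time removed by cases is ignored. With 2,700 subjects per arm (6000 x 0.9 / 2), a 34:14 case split and onset at Day 20 (assumed), it gives h = 0.9934 to Day 180 and 0.9942 to Day 90, a VE difference of 0.04 points.

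**The plan's own figure.** With h = 1 and P = 14/48, P/(1 - P) = 14/34 = 0.4118, so VE = 58.8%. The Clopper-Pearson 95.1% limits for P are 0.1691 and 0.4413. These give RR limits of 0.2035 and 0.7897, and VE limits of 21.0% and 79.6%. Protocol Table 15 is reproduced.

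**Effect of h.** Since h multiplies the RR and both its limits, the lower VE limit is 1 - 0.7897h. It equals 20% at h = 0.80/0.7897 = 1.013.

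**Dropout after Day 90.** If a fraction d of an arm leaves at day t, mean follow-up is (1 - d) x 180 + d x t as written. With a Day 90 cap it is 90 for any t above 90.

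- Exits at Day 91, SA4Ag 8%, placebo 4%: placebo mean = 0.96 x 180 + 0.04 x 91 = 176.44; SA4Ag mean = 0.92 x 180 + 0.08 x 91 = 172.88; h = 1.021.
- The same fractions spread evenly over Days 91-180 (mean exit Day 135.5): 178.22/176.44, h = 1.010.
- Fractions reversed between arms, exits at Day 91: 172.88/176.44, h = 0.980.

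**Dropout before Day 90.** The share of an individual's follow-up lost by leaving at day t is 1 - t/180 as written and 1 - t/90 if capped. The first is larger for every t between 0 and 90; at Day 45 it is 75% against 50%. With exits at Day 45, SA4Ag 10% and placebo 5%:

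- as written: h = 173.25/166.50 = 1.040;
- capped: h = 87.75/85.50 = 1.026.

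**Results at 14/48.**

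| Assumed dropout (SA4Ag vs placebo) | h as written | VE (lower limit) as written | h capped | VE (lower limit) capped |
|---|---|---|---|---|
| Equal amount and timing | 1.000 | 58.8% (21.0%) | 1.000 | 58.8% (21.0%) |
| Day 91, 4% vs 2% | 1.010 | 58.4% (20.2%) | 1.000 | 58.8% (21.0%) |
| Day 91, 8% vs 4% | 1.021 | 58.0% (19.4%) | 1.000 | 58.8% (21.0%) |
| Spread over Days 91-180, 8% vs 4% | 1.010 | 58.4% (20.2%) | 1.000 | 58.8% (21.0%) |
| Day 91, 4% vs 8% | 0.980 | 59.7% (22.6%) | 1.000 | 58.8% (21.0%) |
| Day 45, 10% vs 5% | 1.040 | 57.1% (17.8%) | 1.026 | 57.7% (about 19.0%) |

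**At the futility boundary.** For 11 SA4Ag cases in 24, SAP Table 1 gives VE 15.4% with a lower limit of -105%. Applying h = 1.021 gives 13.6% and -109%.

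**The case against.** The best counter-argument is that little depends on this. The study is double-blind with a single dose given before surgery, so there is no particular reason to expect late dropout at twice the rate on one arm. Balanced dropout cancels in h. The 8% against 4% example crosses 20% only when every exit falls on Day 91; spread over the later period it does not. It also places a large part of the planned 10% dropout after Day 90. All of that stands, and the example should be read as a stress case.

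A reader might infer that the definition could change the trial's efficacy conclusion. The documents do not support that. The 20% criterion belongs to the primary binomial analysis, which does not use h, and SAP Section 8.1.1 attaches no threshold to the follow-up-time analysis. SAP Section 8.1.3.5 also records that the study met its futility criterion at the interim analysis in December 2018, so a borderline success at 14/48 is not what this SAP will analyse.

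A reader might also infer that stretching person-time to Day 180 waters down early dropout. The arithmetic shows the opposite: early dropout gets too much weight.

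The objection does not remove the mismatch. SAP Amendment 5, dated 22 August 2019, comes after the futility result and keeps this analysis for both 90-day endpoints, so the reported person-time would still be the wrong one.

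**Conclusion.** The point holds in a limited form. For the primary endpoint and S aureus SSI within 90 days, the case window and the person-time window differ, and the written rule gives an h that is wrong for those endpoints whenever dropout is unbalanced. The definition broadly suits the two 180-day secondary endpoints, so calling the whole analysis wrong would go too far.

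The size is small: about 0.4 VE points for a 2-point imbalance at Day 91, and about 2 points in an extreme case (10% on one arm, none on the other). The direction depends on which arm loses more subjects. These sizes rest on assumed dropout splits and on 14/48 as an illustration. This is wrong as written for the 90-day endpoints in this sensitivity analysis only, and minor in importance.

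**What to change.** In SAP Section 8.1.1, end follow-up at the earliest of the endpoint's window end (Day 90 or Day 180), study completion, dropout, or onset of a case of the endpoint being analysed. Tying case onset to the endpoint under analysis removes a second ambiguity, since the present text does not say which case ends follow-up. The Day 180 limit is also useful for the 180-day endpoints, because the Visit 6 window runs to Day 192 (Protocol Section 6.3.5).

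The cost is one phrase in the SAP and one line of derivation code. No new data are needed, and the primary analysis does not change.
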